Appendix 1: Tools

Appendix 1a: Shared Labor and Planning Delivery Board

rnal:
:
ress:
assessment:

Appendix 1b: Admission Decision Aid Admission Decision Aid

Use this tool after assessment to help confirm whether admission is necessary.

1	
u	,

Consider: Is admission currently indicated?

CATEGORY	REASONS TO ADMIT	REASONS TO DEFER ADMISSION
MATERNAL	 Observation requires a labor and delivery room Not coping well with early labor and ambulatory strategies are not effective Pain relief requires admission (regional anesthesia) Inducing labor 	 Observation does not require a labor and delivery room Not coping well with early labor but ambulatory strategies are effective Previous history of precipitous labor Social considerations about sending home
FETAL	 Observation requires a labor and delivery room Membranes have ruptured any gestation < 37 weeks gestation ≥ 37 weeks and GBS positive Inducing labor 	 Observation does not require a labor and delivery room Membranes have ruptured gestation ≥ 37 weeks and GBS negative
PROGRESS	 In active labor – regular contractions and ≥ 4 – 6 cm dilated 	 Not in active labor but has documented cervical change with regular contractions

2 Consider: Which options can support the laboring person if deferred?

COUNSELING	PHYSICAL	CLINICAL
 Explain the benefits of deferred admission Provide encouragement Provide advice on relaxation and breathing techniques 	 Provide an alternate labor space (if available) Facilitate position change, movement, ambulation Provide hydrotherapy (tub/bath/shower if available) Offer hydration and nutrition Provide tools to aid labor (birth ball or rebozo if available) 	 Administer pain relief non-pharmacological (water injections, TENS, hot and cold therapy, acupuncture, massage) pharmacological (non-opioid analgesia, therapeutic sleep) Consider laboratory testing or imaging

Appendix 1c: Delivery Decision Aid

Delivery Decision Aid

Use this tool to guide team discussion when considering operative delivery. All team members should be present.

Ask aloud: "What is the reason for considering delivery?"

2 Confirm aloud: Have the minimum criteria for that indication been met?

CATEGORY	INDICATION	MINIMUM CRITERIA
MATERNAL	Request	
FETAL	Intolerance of labor	 Any of: Bradycardia Recurrent decelerations and absent variability Recurrent decelerations that do not improve with resuscitation and remote from delivery Tachycardia that does not improve with resuscitation and remote from delivery
PROGRESS Failed induction of labor Active phase arrest Active phase arrest Second stage arrest Second stage arrest	Either: • Latent phase lasted ≥ 24 hours • Oxytocin administration ≥15 hours with ruptured membranes	
	Active phase arrest	No cervical change with ruptured membranes and ≥ 6 cm dilated with either: • Adequate contractions (>200 MVU) ≥4 hours • Oxytocin administration ≥6 hours
	Second stage arrest	Either: • Multiparous and pushing ≥2 hours • Nulliparous and pushing ≥3 hours

Ask aloud: "Are there options that will allow more time for labor?"

(see other side for suggested options)

Yes: Discuss options and make a plan.

No: Discuss risks and benefits of operative delivery and answer any questions.

Delivery Decision Aid: Options for more time

The following options may offer reassurance and provide additional time for labor and vaginal delivery.

CATEGORY	OPTIONS
MATERNAL	 Provide emotional support (communication with the mother, encouragement, breathing and relaxation techniques)
	 Provide physical support (movement, positional change, hydrotherapy, acupuncture, touch techniques, massage)
	Adjust environment (decrease stimuli)
	 Administer pain relief non-pharmacological (hydrotherapy, TENS, hot and cold therapy) pharmacological (non-opioid analgesia, nitrous oxide, opioid analgesia, regional anesthesia)
	Order laboratory testing or imaging
	Consult with additional clinicians
FETAL	Facilitate movement and positional change
	 Assess well being (change fetal heart monitoring method, perform scalp stimulation)
	 Pause augmenting agent (stop oxytocin)
	 Reverse augmenting agent (administer tocolytic)
	Resuscitate (hydration, oxygen, amnioinfusion)
	Consult with additional clinicians
PROGRESS	Facilitate movement, ambulation, or relaxation (rebozo, walking path, birthing ball, hydrotherapy, reduce environmental stimuli)
	Augment labor
	Adjust dose of oxytocin
	Confirm contraction strength (IUPC)
	Consult with additional clinicians

Appendix 2: Tool Development and Adaptation

Tool Development

This program was developed using a year-long, rigorous human-centered design process that included expert validation and rapid cycle testing. Through a comprehensive review of the peer-reviewed literature, gray literature, and professional organization guidelines evidencebased strategies were identified to reduce harm from overuse of cesarean deliveries. Using expert consultation with approximately fifty key leaders from clinical obstetrics (nurses, midwives, obstetricians, anesthesiologists), patient advocacy, health services research, and implementation science, we prioritized the strategies based on their strength of evidence, impact, ability to be operationalized through simple tools, and sensitivity to context. As a result of this process, strategies that preserved labor progress and minimize preemptive cesareans for inadequate labor progress in the absence of other concerns were prioritized.

Clinical workflow process maps and logic models were developed to identify opportunities to operationalize these strategies, including the specific opportunity to improve team decision-making. A second expert consultation session surfaced four previously described behaviors. Using interviews with clinicians, and rapid cycle testing in simulation, a set of care planning and decision aids to support these behaviors at admission, during labor, and at delivery were developed.

The tools organize available pertinent data and care management options using a patient facing shared planning board that can create accountability between the laboring woman, nurse and delivering provider and two decision aids to support the decisions to admit a woman to a labor and delivery room and to deliver her baby operatively. The decision aids embed guidelines for labor management from national professional organizations, but do not direct specific care management options. In addition to use of these aids by the care teams, an implementation model has been developed which will be evaluated for implementation fidelity and track progress towards patient safety goals.

Tool Adaptation

Throughout the implementation process, the local site implementation team will make adaptations to the tools and implementation processes based upon their context, resources, and early experiences with training on, coaching about, and using the tools. There are three categories of adaptations that can be made while maintaining implementation fidelity:

- 1. No Adaptation: Features that are essential to the four behaviors that constitute the program objectives and therefore cannot be adapted without altering the program objectives.
- 2. Ariadne Labs-Guided Adaptation: Features that have major impact on core behaviors but can be adapted by local sites with Ariadne Labs support to ensure adequate implementation, tracking, and measurement of the changes.

3. Site Guided Adaptation: Features that are not essential to the core behaviors and will be best adapted to local contexts and preferences.

ΤοοΙ	No Adaptation	Ariadne Labs-Guided Adaptation	Site Guided Adaptation
Labor and Delivery Planning Board	Conversations between laboring woman, nurse, and provider	In person vs. phone conversations	Lead roles for different elements of conversations
	Conversations in MFP format	Identifying critical moments for conversations	Location of whiteboard in the labor room
	Updating of whiteboard at each key moment conversation	Modifying elements of the labor and delivery planning board	
Admission Decision Aid		Indications for admission may vary with site and context	Plan options may vary according to availability at sites
Delivery Decision Aid	Indications for delivery		Lead roles for different elements of verification
			Team members present for verification
			Plan options if do not meet verification indications

Ariadne Labs-Guided Adaptations will be discussed with the Ariadne Labs Project Team and local site teams before implementation and will be rolled out at set points in time to facilitate measurement of the changes and acceptability. Site Guided Adaptations will be allowed to happen organically based on the preferences of the local champions, super-users, and frontline staff. All adaptations will be tracked by the Ariadne Labs Project Team along with the justifications for each adaptation as part of our program evaluation.

Appendix 3: Patient Record Data Measures

Patient level data and/or calculated measures may come from ICD-10 codes or from other fields in the clinical record, depending on the variable and the existing data infrastructure and analysis processes at the hospital. The Ariadne Labs Project Team will request that the hospital team provides these data on a monthly basis.

The Ariadne Labs Project Team will use these data to calculate indicators, such as rates and counts, to include in reports for the study team, managers, clinicians, and any other people at the hospital involved in the project. The reports will focus on primary outcomes for impact of the quality improvement initiative, including cesarean delivery rates and other related indicators (i.e. operative delivery rates). We will also monitor selected maternal and neonatal adverse events and co-morbidities in order to identify other potential benefits or harms and provide context to interpret the primary outcome results.

Below are examples of the types of indicators we will report based on the patient level data the hospital team provides. Further below is a full list of the patient level data elements we will request to calculate these indicators.

Procedures

- Cesarean delivery rate
- Operative delivery rate
- Vaginal delivery rate
- Induction rate
- Episiotomy rate

Patient Comorbidities

- Rate of diabetes
- Rate of hypertension
- Cholestasis of pregnancy
- Placenta previa
- Placenta accreta

- Maternal Adverse Events
 - 3rd/4th degree laceration rate
 - Hemorrhage rate
 - Infection rate
 - ICU admission
 - Maternal death

Other

- Indications for cesarean
- Indications for admission
- Length of labor

Neonatal Adverse Events

- Birth trauma rate _
- Rate of Apgar \leq 7 at 5 minutes
- Intubation rate
- NICU admission rate
- Neonatal death

or operative deliveries

Maternal Variables

Maternal ID Month of delivery Year of delivery Maternal age Gestational age Parity Prior cesarean delivery Scheduled cesarean delivery TOLAC Cesarean indication Induction Scheduled induction Admission indication Dilation at admission Labor length First stage of labor length Postpartum stay length **Episiotomy** Third/fourth degree laceration Maternal death Maternal ICU admission Postpartum hemorrhage Massive obstetric hemorrhage Blood transfusion Placenta accreta Placenta previa Unplanned hysterectomy Infection Sepsis Cholestasis Chorioamnionitis Uterine rupture Abruption Acute fatty liver of pregnancy Acute renal failure Amniotic fluid embolism Cardiac arrest Ventricular fibrillation Disseminated intravascular coagulation Deep vein thrombosis lleus Acute heart failure Pulmonary edema

Pulmonary embolism Substance misuse Pre-gestational diabetes Gestational diabetes Chronis hypertension Gestational hypertension Preeclampsia Eclampsia Sickle cell disease Epidural

Neonatal Variables Baby ID Maternal ID Mode of delivery Presentation Ventilation resuscitation within the first 72 hours Cardiopulmonary resuscitation within the first 72 hours Cardiac arrest Cephalohematoma Hypoglycemia Stillbirth Neonatal death NICU admission Neonatal transfer Unexpected newborn complications Apgar at 1 min Apgar at 5 min Meconium aspiration syndrome Birth trauma Intracranial hemorrhage Encephalopathy Hypotension Pneumonia Seizures Sepsis Transfusion Preexisting condition Intubation Continuous positive airway pressure (CPAP)

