This project will evaluate and support the implementation of a process improvement program that is designed to improve vaginal delivery rates to enhance the safety and experience of care. The program was developed through a one-year design effort at Ariadne Labs that included literature review, expert validation, workflow mapping, feature selection, prototyping and rapid cycle testing.

2. Statement of the Problem

The goal is to improve vaginal delivery rates to enhance the safety and experience of care. Cesarean delivery rates have been selected as the primary patient safety indicator because overuse of cesarean deliveries is a national concern and cesarean reduction is a top priority among the American College of Obstetricians and Gynecologists, Society for Maternal Fetal Medicine, and American College of Nurse Midwives.

To date, professional efforts to safely reduce cesarean rates focus on improving clinical knowledge. Policymakers, payers and purchasers tackle addressing misaligned incentives through payment and malpractice reforms. However, emerging research at Ariadne Labs suggest a third, previously unaddressed root cause -- unintentional errors due to system complexity.¹²

This project aims to mitigate errors rooted in system complexity by addressing three types of challenges that can influence team performance:

I. Timing of Key Decisions

Optimizing the timing of when to admit patients to a labor and delivery room or when to deliver operatively has a substantial impact on the likelihood of cesarean delivery independent of other risks and preferences. Guidelines on when to do a cesarean delivery are imprecise. In emergent situations, obstetric clinicians (nurses, midwives and doctors) agree about when to perform a cesarean delivery, but reasonably disagree about when to act *to prevent* an emergency. In the absence of a communication process to ensure appropriate decision makers are considering all of the pertinent information *and* using a common decision

framework, disagreements can go unrecognized or unresolved. As a result, even wellintended, well-trained and board-certified clinicians perform surgeries that appear to be potentially avoidable, and even harmful, in retrospect.

II. Shared Information and Decision Making

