Specifically, the Admission Decision Aid 1) **improves precision** by separating the reasons for admission into three distinct categories: maternal, fetal, and progress, 2) **improves accuracy** by distinguishing between patients who need to be admitted versus those whose admission can be deferred and 3) **organizes the care options** which can be reviewed with other members of the care team when constructing care plans to manage the care of laboring women.

iii) Delivery Decision Aid (Appendix 1c)

The Delivery Decision Aid is a one-page tool intended to improve the accuracy of decisions to intentionally deliver a baby (via cesarean or operative vaginal delivery) instead of allowing labor and delivery to proceed. The tool is to be used by the labor nurse and delivering provider in front of the laboring woman during a team huddle when clinicians are considering

whether an operative delivery is indicated or when any member of the care team would like to review the care options.

The Delivery Decision Aid 1) improves **precision** by separating the reasons for performing an operative delivery into three distinct categories: maternal, fetal, and progress), 2) **requires reliability and accountability** (ensuring the minimum criteria to deliver have been confirmed each time this decision is made, and requiring that this confirmation and decision process occurs verbally with the nurse, delivering provider, and woman all present), and 3) **organizes the care options** which can be reviewed with other members of the care team when constructing care plans to manage the care of laboring women.

III. Sites

Four sites have been selected to partner with Ariadne Labs to trial this process improvement program. We have aimed for diversity in the choice of site which includes the following variables: geography, rural/urban mix, facility type (academic health canter, community hospital, critical access hospital etc.) delivery volume, provider mix and patient demographics. Overlying these parameters, we have used four criteria -- specifically high need (facility cesarean rates have room for improvement), willingness to engage in the improvement program with capacity to support the implementation of the program and broader relationships that can lead to spread of the program regionally and nationally.

The criteria are described in more detail below.

NEED: Hospitals with NTSV 1 cesarean rates above the HealthyPeople 2020 target of 23.9%

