WILL: Site leadership commitment at the executive, service line, and front-line levels

CAPACITY: Site infrastructure to support quality improvement activity, including oversight responsibility for quality, data tracking for quality assurance, and standing quality assurance committees

RELATIONSHIPS: Site has relationships with state perinatal quality collaborative department of public health, or other stakeholders to facilitate spread.

SITE	SPECIFICS	LAUNCH
CONFIRMED		
South Shore Hospital, South Weymouth, Massachusetts	Community hospital, annual delivery volume ~3000, 40% NTSV rate	April 2018
Saint Francis Hospital, Tulsa, Oklahoma	Catholic, not-for-profit health system, annual delivery volume ~4000, NTSV rate 36%	September 2018
Eastside Health Alliance - Overlake Medical Center and Evergreen Health, Puget Sound, Washington	Alliance between a regional non-profit hospital and a public district hospital	January 2019

IV. Implementation Plan

Table 1: Study activities

Table 1: Study activities	1 1		1																		
		QI or	Pre- implementation	12	3	4	5	6	7	8	9	10	11	12	13	14	15	16	17	18()ngoing
Activity	Lead team	research						- h	mp	lem	nen	tati	ion	pei	riod	I					
Identify super-users and champions	Site	QI	✓																		
Small scale implementation	Both	QI	✓																		
Training the trainers	Ariadne	QI	✓																		
Training the observers	Ariadne	QI	✓																		
Installation of tools	Site	QI	✓																		
Widespread training	Site	QI	✓																		
Ongoing coaching & support	Both	QI		✓ ✓	′	\checkmark	\checkmark	\checkmark	\checkmark	\checkmark	\checkmark	\checkmark	✓	\checkmark							
Training evaluation	Site	QI	✓																		
Observations	Site	QI																			
Four 12-hour shifts per week				✓ ✓	′ ✓																
Three 6-hour shifts per week						✓	\checkmark	\checkmark	\checkmark	\checkmark											
Three 4-hour shifts every other week											\checkmark	\checkmark	\checkmark	~	\checkmark	~	\checkmark	\checkmark	\checkmark	\checkmark	
Ad hoc as needed for sustainability															·						✓
Patient record data extraction	Both	Both		✓ ✓	✓	✓	\checkmark	✓	\checkmark	\checkmark	\checkmark	✓	✓	\checkmark	\checkmark	\checkmark	\checkmark	✓	✓	✓	✓
Management Surveys	Site	Research	✓																	✓	
Clinician Practice Surveys	Site	Research		✓						\checkmark				\checkmark							
Clinician Acceptability and Feasibility	Site	Research			1					\checkmark				~							
Surveys																					

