- 4. Collection of preliminary data on the relationship between the tools and subsequent implementation on patient outcomes between the use of the tools and corresponding implementation with cesarean delivery rates

As the Quality Improvement Program progresses at each local site, we will collect additional data toward the above aims (Table 4). The three primary endpoints relate to the implementation of the intervention (Primary 1), its acceptability to various groups (Primary 2), and any unintended consequences, including adverse events that could impact patient safety (Primary 3). Additionally, cesarean delivery rates will be monitored at each site to identify any decline as a secondary endpoint. Since this is not an effectiveness trial, the study is not intentionally powered or designed to detect this reduction. The two exploratory endpoints will measure the specific adaptations of the program and any information on how the program succeeds or struggles in various contexts.

Table 4: Endpoints

Primary	1	High fidelity Implementation of the program
	2	Acceptability and feasibility of the program
	3	Patient safety
Secondary		Patient benefit, including program effectiveness at improving vaginal delivery rates
Exploratory	1	Adaptation of the program for improvement
	2	Determinants of how program successes and failures

The aims and endpoints will be measured with a variety of outcome measures, as shown in Table 5. Each aim maps to an endpoint, which is paired with a specific research question. The table also lists the specific measures and data sources we will use to address each question and the domains covered in each data source.

Table 5: Aims, endpoints, outcomes, data sources, and domains

Aim	Endpoint	Implementation question	Outcome measures	Data sources	Domains
1. Adaptation of the tools	Primary 1	How are the four core behaviors	Quantity and quality	Observations	Involvement of minimum team
and implementation strategy to optimize		implemented?	of core behaviors	Clinician Practice Surveys	Incorporation of woman's input
practice of the four			performed	Clinician Knowledge and	Precision of MFP distinction
behaviors				Attitudes Survey	Shared expectations
				Clinician Interviews	
				Patient Surveys	
	Primary 1	Are the tools implemented?	Quantity of tool use	Observations	Team huddle occurrence
				Clinician Practice Surveys	Whiteboard use
				Patient Surveys	Admission decision aid use
					Delivery decision aid use

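### Does the missing denominator, and the loose primary label, for the cesarean delivery rate call for a change to the plan?

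*Combined protocol and SAP*

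**What the plan says.** The cesarean rate is described in three ways. Section 4.I states that "cesarean delivery rates will be monitored at each site to identify any decline as a secondary endpoint". Table 4 agrees: its three primary endpoints are fidelity of implementation, acceptability and feasibility, and patient safety. Section 2 says "Cesarean delivery rates have been selected as the primary patient safety indicator". Appendix 3 says "The reports will focus on primary outcomes for impact of the quality improvement initiative, including cesarean delivery rates and other related indicators", and adds that adverse events and comorbidities are monitored partly to "provide context to interpret the primary outcome results".

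Appendix 3 gives no numerator, denominator or population for the rate. The list containing it opens with "Below are examples of the types of indicators we will report".

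Section 3.III uses a different measure. Sites were sought with NTSV "cesarean rates above the HealthyPeople 2020 target of 23.9" percent. Two site entries carry figures: "annual delivery volume ~3000, 40% NTSV rate" and "annual delivery volume ~4000, NTSV rate 36" percent.

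Two passages define populations. Section 3.IV applies the tools to all women except those with a scheduled cesarean or an induction for fetal loss. Section 4.II limits patient participants to live births after spontaneous or induced labor, with scheduled cesareans excluded. Section 4.IV defers details to a later statistical analysis plan and expects descriptive statistics with no tests for causal inference.

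**The concern.** A rate monitored for a decline needs a stable denominator. If all births are counted, the rate mixes women for whom the tools are used with women for whom they never are. It can then rise or fall because the share of scheduled cesareans changed, with nothing different in labor care. Nor could such a rate be set beside the 40% and 36% NTSV figures, which are the only site cesarean figures in the documents.

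The wording adds to the doubt. A reader who starts from Appendix 3 could take the cesarean rate as the primary outcome and patient safety as background, the reverse of the order in Section 4.I. At stake is whether a reported trend can be read as a change among women who labored with the tools in use.

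**Working it through.** The plan gives no sample size, power, alpha or baseline count for this endpoint, so there is no figure to reproduce. The check is a comparison of sections, followed by an illustration of size.

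**1. Which population would an analyst use?**

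| | Section 3.IV, tool use | Section 4.II, research eligibility |
|---|---|---|
| Scheduled cesarean | out | out |
| Fetal loss | inductions for fetal loss out | out (live birth required, stillbirth excluded) |
| Neonatal death | in | out |
| Age limit | none stated | 18 or older; 15 or older at one site |

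The two sections agree on scheduled cesareans, which drive the concern. They differ on age, on neonatal death and on details of fetal loss. The documents give no counts for these groups.

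**2. Can the restricted rate be derived?** Yes. Appendix 3 requests scheduled cesarean, induction, stillbirth, mode of delivery, gestational age, parity, presentation, and maternal and baby IDs that can be linked. The first four give a rate without scheduled cesareans or stillbirths. Mode of delivery and the remaining fields largely allow an NTSV rate, with singleton births inferred from one baby ID per maternal ID in a delivery. The limit on comparison lies in the indicator as named, not in the data.

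**3. Does the label alter the hierarchy?** Section 4.I and Table 4 are where endpoints are assigned, and they agree with each other. The Appendix 3 sentence concerns reports on the impact of the quality improvement initiative, which the protocol keeps apart from the research (Section 3 against Section 4, and a column in Table 1). Section 2 is a problem statement.

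**4. How large is the effect if all births are used?** Let s be the scheduled-cesarean share of births and u the cesarean rate among the rest. Neither is in the documents; assume s = 10 to 20% and u = 20 to 30%, and ignore fetal-loss inductions. The all-birth rate is R = s + (1 − s)u.

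- u falls 5 points, s fixed: R falls by 5(1 − s), which is 4.5 points at s = 0.10 and 4.0 at s = 0.20. So 80 to 90% of the change shows.
- s rises 2 points, u fixed: R rises by 2(1 − u), which is 1.6 points at u = 0.20 and 1.4 at u = 0.30.
- Rise in s that fully hides a 2-point fall in u: 2(1 − s)/(1 − u + 0.02). For (s, u) = (0.10, 0.20), (0.10, 0.30), (0.20, 0.20) and (0.20, 0.30) this is 2.20, 2.50, 1.95 and 2.22 points.

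For scale, take the two stated volumes. Births per month are 3000/12 = 250 and 4000/12 = 333. Removing 10 to 20% leaves 200 to 225 and 267 to 300. The 95% half-width 1.96·√(u(1 − u)/n) runs from 4.5 points (u = 0.20, n = 300) to 6.4 points (u = 0.30, n = 200) per month. Dividing by √12 = 3.46 gives 1.3 to 1.8 points over 12 months.

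**The case for a change.** The strongest case for a change has three parts.

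First, Section 4.II lists exclusions for patient participants, and nothing says that they govern the record extract. Appendix 3 asks for scheduled cesarean, stillbirth and neonatal death, so the extract is evidently wider than the eligibility criteria. This stands: no sentence ties the record-based rate to either population. But a wide extract is needed for the safety endpoint, which covers neonatal mortality, and does not imply that the cesarean rate will be computed on all of it.

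Second, the analysis plan is due only before the final analysis, while data are requested monthly and reports go to the sites during implementation. Appendix 3 also lets some measures depend on a hospital's own processes. This stands in part. Early reports could use a cruder rate, but Appendix 3 has the central project team calculate the indicators from patient-level data, and a crude interim rate can be recomputed later.

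Third, a masked 2-point fall would matter over a year, when the half-width is 1.3 to 1.8 points, even though it is lost in the noise of one month. That is true under the assumed values. It needs an all-birth rate, an opposite shift in the scheduled share of about the same size, and nobody looking at that share although the field is requested.

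Reporting an NTSV rate as well would be useful but is a preference. A measure used to choose sites need not be an outcome, and NTSV leaves out multiparous women, whom the tools also cover.

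**Conclusion.** The gap is real but is ordinary detail for the promised analysis plan. An analyst who follows either population in the protocol leaves out scheduled cesareans, has the fields to do so, and can show the scheduled share alongside. The remaining choice between Sections 3.IV and 4.II concerns age limits and births with fetal or neonatal death; the documents do not show that it would alter a conclusion. The primary wording in Section 2 and Appendix 3 is a slip of language that leaves Table 4 in force.

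The consequence is bounded by the kind of endpoint: secondary, descriptive, explicitly unpowered, with no test attached. This rests on the analysis plan being written as promised, and the sizes rest on the assumed scheduled share and cesarean rate. No change to the plan is needed.
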